All determinations of cholesterol and triglycerides in whole serum and in HDL will be carried out in the Core Lipid Laboratory of the Atherosclerosis Score at Columbia. [name] is the Director of this laboratory, which is a participant in the Standardization Programs of the Centers for Disease Control. Cholesterol and triglyceride levels will be determined by enzymatic methods using the Hitachi 705 automated spectrophotometer. The interassay coefficients of variation for these two measurements are less than 3% at present. Whole HDL cholesterol will be measured at the precipitation of plasma apo-B-containing lipoproteins at 10 gm per liter Dextran sulfate and 0.5 M magnesium Mg Cl₂ (0.91 mg per ml and 0.045 M final concentrations, respectively).

2. Louisiana State University

All routine lipid analyses (total cholesterol, triglycerides) will be performed on the Beckman Synchron CX5 automated chemistry analyzer. HDL cholesterol is performed in the Beckman TH5 after precipitation of the non-HDL fractions by Dextran sulfate (50,000 MW) (DMA, Dallas, TX) following the protocol of Warnick, et al. Assay controls by DMA are used to verify accuracy. LDL cholesterol is calculated using the Friedewald formula.

For automated analyses, daily quality control is performed prior to all analyses which will be run on that day. Acceptable results must be obtained on quality control before any results are allowed to be reported. The results are logged into a computer bases' quality control monitoring package (Lyphline, BioRad Laboratories). Results for the intralaboratory comparisons by BioRad for lipid analyses have been very good. For cholesterol, there is a cumulative CV of 1.5% for level 1 and 2.5% for level 2. Comparison with other Beckman CX5 users shows the SDI is -1.0 and -0.9 for levels 1 and 2, respectively (-2.0 and +2.0 acceptable). For triglyceride, there are cumulative CVs of 1.8% and 3.7% for levels 1 and 2. The SDIs are negative for 0.1 and 0.2 when results are compared to others CX5 users. For HDL, controls are assayed from DMA. They are consistently within the acceptable ranges for these values. CVs are 2.9% and 6.4% for levels 1 and 2.

3. The MI Bassett Research Institute

Lipid profiles consist of measurement of total cholesterol, triglycerides, HDL cholesterol after precipitation of apo-B-containing lipoproteins using 50,000 MW Dextran sulfate. LDL cholesterol is calculated today using the Friedewald formula. All analyses are done on a Roche MIRA random access automated analyzer. Cholesterol and HDL cholesterol are assayed by enzymatic method based on a cholesterol esterase and a cholesterol oxidase system using a peroxidase / 4 amino antipyrene detection system. This is manufactured as Roche reagent for cholesterol (Roche Diagnostic Systems). For HDL cholesterol detection, non-HDL lipoproteins are precipitated by treatment of 500 microliters of serum with 50 microliters of Dextran sulfate (Sigma Chemical). Triglycerides are assayed by Sigma Chemical triglyceride reagent based on hydrolysis by lipase and detection of glycerol by glycerol kinase, coupled with glycerol-1-phosphate oxidation to produce peroxide, which is detected by peroxidase conversion of the aminoantipyrene to quinonemia.

Calculation of cholesterol is based on a serum-based calibrator certified for accuracy by cross-over with Abell-Kendall reference method. Calibration is done in triplicate once a month. Calibration of triglyceride is based on reaction with pure glycerol expressed as equivalent triolein (Sigma Calibrators). For total cholesterol, two levels of quality control material (from Dade) are included with each run. For HDL cholesterol, two levels of quality control material are precipitated and analyzed with each run. For triglyceride, two levels of quality control material are included in each run. A run is considered out of control, using Westgard rules and precision ranges based on MTP guidelines (3% for total cholesterol, 5% for triglycerides, 3% for HDL cholesterol). If it runs out of control, the entire run is repeated.

4. University of Minnesota

Cholesterol is measured on a Roche Cobas FARA analyzer using Boehringer Mannheim enzymatic reagent. A frozen serum pool which has been measured on multiple occasions by the Abell-Kendall method is used as calibrator. Accuracy of cholesterol measurements are also verified by the CDC and are in close agreement with their reference Abell-Kendall method with fresh patient samples. Total serum triglyceride is measured on a Roche Cobas FARA analyzer using Boehringer Mannheim GB reagent and calibrator. This method gives a "true" triglyceride level which has been corrected for free glycerol concentrations. Triglyceride measurements are standardized by the Centers for Disease Control (CDC) Lipid Standardization Program and are in close agreement with the CDC reference triglyceride method. LDL cholesterol is estimated by the Friedewald formula. This equation assumes a ratio of five for plasma triglyceride to the VLDL cholesterol; while this ratio is correct for the typical American diet, it may change for other proposed research diets.

The HDL cholesterol is measured enzymatically after precipitation of VLDL and LDL with Dextran sulfate (molecular weight 50,000) and magnesium chloride. The method is the same as described by Warnick, et al. We have chosen the Dextran sulfate/magnesium precipitation method over the Heparin/Manganese procedure because Manganese interferes with enzymatic cholesterol methods and must, therefore, be removed with sodium bicarbonate. This adds additional steps and imprecision to the method. In addition, the Dextran/Magnesium method is less sensitive to variations in temperature and centrifugation.

C. Apoprotein A-1 and BIOO (MIBH)

The analytical method is rate nephelometry using antisera specific for Apo-A1 or Apo-B-100. The formation of antigen-antibody complexes are monitored with time; the initial reading of light scatter serves as a baseline for change. Instrument monitors the rate of change and rejects any sample where change in turbidity with time is outside an acceptable margin of error, thus assuring that the presence of particulate matter drifting through the measurement field or the occurrence of lipemia does not produce artificially modified results. Analysis is performed on a Beckman Array using Beckman reagents, calibrators, controls (Beckman Instrument Company, Fullerton, CA). Fresh or frozen serum may be used. Reagents are polyclonal antisera specific for either apolipoprotein A-1 or apolipoprotein B-100. Titers of the antisera are determined by the manufacturer and preparation is optimized for reaction in the volumes of buffer and sample used with the Array system. Each lot of antisera is accompanied by programming information which is entered into the instrument to fit the calibration curve and set the margin of error allowable for the rate of reaction. Calibrators are standardized to the internationally developed reference material designated by CDC-IUIS (Centers for Disease

Control and International Immunological Society). The instrument is calibrated every two weeks using this material. Control materials are included at the beginning, middle, and the end of all runs to assure reproducibility of results.

Quality control samples are included at the beginning and the end of each run and are analyzed in duplicate. If the average value is not within the ± 2 standard deviation range for the QC samples or if reproducibility in these samples is unacceptable (samples at the end of the run deviated by more than one standard deviation from those at the beginning), the entire run is repeated. The precision for Apoprotein A-1 at 117 mg per deciliter over the long-term (run to run) is 4.9% and within run is 0.7-1.8%. Apo-B 100 precision at 170 mg per deciliter over the long run (run to run) is 3.8% and within run is 0.3-0.9%. The samples that give an error signal, indicating that they fall outside an acceptable time course development of turbidity are diluted and reanalyzed to assure this reaction did not occur at antigen or antibody access.

D. Lipoprotein a (MIBH)

Analytical method is an ELISA (Enzyme Linked Immunosorbent Assay) using the Macra LPa kit manufactured by Terumo (Elkton, MD). Monoclonal antibody to Lp (a), immobilized on microtiter wells, serves as the capture antibody. Bound Lp (a) is detected using a monoclonal anti LP (a) antibody conjugated with horseradish peroxidase. The complex is detected and quantified by chromagen formation upon incubation of peroxide and o-phenylenediamine substrate. A 100 microliter aliquot of serum, stored at -80°C , is used for this assay. The antisera, calibrators, and controls are provided by Terumo (Elkton, MD) in their Macro LP (a) kit. ELISA plates are read on an automated ELISA plate reader, Dynatech model MR600 set to monitor at 492 nanomoles. A calibration curve, consisting of six ampules ranging from 0-80 mg/dL Lp (a) is run in each batch. Each calibrator is run in duplicate and averaged to generate a standard curve. Each sample is analyzed in duplicate.

Two quality control samples are included in each run. If these do not match the target value within ± 2 standard deviation, the run is repeated. The precision of LP(a) at 15 mg per deciliter on the long term (day-to-day) is 3.9% and within run is 1.4%. LP(a) of 36 mg per deciliter has a long-term precision (day-to-day) of 3.8% and within run of 1.8%. Samples of LP(a) concentrations above the highest calibrator or absorbing at over 2.0 absorbing units are diluted 1-to-1 with saline and repeated on another run.

E. Coagulation Factors

1. Fibrinogen

Fibrinogen will be measured by the clot-rate method of Clauss, using a semi-automated instrument, the ST4 from Stago. The assay will be standardized using the College of American Pathologists Standardized Reference Plasma, which the UV laboratory helped establish.

In addition to outside quality assurance programs, such as the Coagulation Program of the College of American Pathologists, quality control will be established with three control materials (normal, elevated, and low) and so-called Westgard Rule (the multi-rule Shewart QC System) will be applied. Longitudinal drift will be assessed using lyophilized

control plasma. In one recent large study in the UV laboratory, the fibrinogen assayed at an average monthly CV of approximately 3.09% and blind duplicate analyses included the technical error of 7.4% with a correlation calibration of 0.8727. The fibrinogen assay will be done each test plasma in duplicates at one dilution (1/10). If the fibrinogen concentration is too high, the sample is assayed again at 1/20, 1/40 dilution. Assay requires a minimal of 0.25 ml of citrated plasma.

2. Factor VII Activity

Factor VII activity will be assessed using one-stage clot-rate assay based upon the prothrombin time, using immunodeficient human plasma. The thromboplastin will be human placental thromboplastin, and the assay will be standardized using World Health Organization reference plasma. The semiautomated Coag-A-Mate X2 instrument from General Diagnostics will be used.

Quality control will be established with two control plasmas (both approximately normal) and so-called Westgard Rules (a multi-rule Shewart QC system) will be applied. Longitudinal drift will be assessed using lyophilized control plasma. In one recent large study in the UV laboratory, the Factor VII assay had a monthly average CV of approximately 5.31% and blind duplicate analyses indicated a technical error of 6.2% with a correlation of coefficient 0.9133. Factor VII assay will be done on each test plasma as singleton measurements on each of two dilutions, 1/20 and 1/40. If the Factor VII concentration is too high, the sample is assayed again at a higher dilution. The assay requires a minimum of 0.50 ml of citrated plasma. The plasma should be centrifuged as soon as possible following phlebotomy, using at least 30,000 g min of centrifugation. Ideally, the sample should not be cooled on ice following phlebotomy, nor should the centrifugation occur at 4°C, but rather at room temperature. Factor VII may be activated in the cold and this should be avoided whenever possible. Following preparation of plasma, the samples should be frozen as soon as possible. When thawed, the samples will be thawed quickly and assayed immediately to minimize the possibility of Factor VII activation.

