8. PAI-1

Plasminogen activator inhibitor-1 (PAI-1), a major plasma regulator of fibrinolysis, is associated with plasma lipids, especially triglycerides, and has been shown to be elevated in those with prevalent CVD. It is also elevated in those who go on to have a second myocardial infarction compared to those who do not. Other than that, there are no prospective data concerning PAI-1, but several studies are ongoing at the present time. PAI-1 is elevated in diabetics and some have proposed that this is due directly to plasma insulin. However, clinical studies have failed to reveal an acute response to insulin, so the insulin connection is currently in question. A second candidate is the plasma triglyceride level, since this is responsive to insulin to a certain extent, and might provide the link to insulin seen cross-sectionally. Since there is little known about the influence of diet on PAI-1, the studies proposed here may shed some light on this issue. PAI-1 levels appear to have a diurnal cycle, requiring the collection of samples between 7 and 10 a.m.

9. Baseline chemistry and TSH

Liver function tests (AST, ALT), renal profile (BUN, creatinine), glucose, and thyroid stimulating hormone (TSH) are performed at baseline to identify individuals with conditions which could modify dietary responsiveness to fats and cholesterol. Individuals who have these conditions should not participate in the study for both scientific and safety reasons.

10. Hematology

Hematocrit, hemoglobin, and white blood cell count should be monitored at baseline to assure that the subject will not suffer untoward effects from serial phlebotomy.

11. Other analytes considered

Additional analytes considered include glucose and insulin, platelet factor 4, and beta thromboglobulin, and a number of other coagulation parameters. For Study I, it was decided that the protocol for laboratory analyses would be rather simple. However, a large number of aliquots of serum plasma and buffy-coat cells will be carefully stored, to allow later analyses. Similarly, 24-hour urine collections will be of interest, but are put off to later studies, especially those which have fats which may affect prostaglandin metabolism.

II. BLOOD COLLECTION -- AN OVERVIEW

A. Overview

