The DELTA Study requires collection of approximately 25.5 ml of blood from participants at baseline and approximately 36 ml of blood four times at the end of each diet phase. Additional samples may be required from premenopausal women. Since the study depends on the voluntary participation of subjects, both initially and in follow-up, every effort must be made to make the entire procedure as easy and painless as possible, both for the participants and for the field center personnel.

The following schematic describes the blood sampling for a single study subject (Figure 1).

The LDX Capillary Blood Analyzer by Cholestech Corporation (Walnut Creek, CA) will be used for subject screening. This instrument provides accurate and rapid (three minute) results for total and HDL cholesterol and triglycerides (if fasting) at reasonable cost. The Cholestech Corporation has agreed to donate one machine per field center and 500 cassettes at cost for this project. Publications which describe subject screenings should acknowledge use of this instrument in the Methods section and the contribution of Cholestech Corporation in the Acknowledgements. Technicians using this instrument should receive training by OSHA regulations, sample collection technique, and the proper use of this equipment.

Recruitment

Capillary Blood Total and HDL

Baseline	Baseline Package
Diet A, Week 5,6,7,8	Four endpoint packages
Diet B, Week 13,14,15,16	Four endpoint packages
Diet C, Week 21,22,23,24	Four endpoint packages

The baseline package contains serum for a chemistry profile and TSH (6 ml), EDTA plasma for hematology (3.5 ml), EDTA - plasma for buffy-coat (10 ml), and serum for a fasting lipoprotein profile (6 ml) for a total of 25.5 ml of whole blood.

The endpoint package contains a serum for lipid profile, apolipoproteins, and aliquots (9.5 ml), a tube for serum aliquots (9.5 ml), a citrate-plasma tube at room temperature (4.5 ml) for Factor VII, a second citrate-plasma tube at 4°C (4.5 ml) for fibrinogen and PAI-1, and an EDTA-plasma tube at 4°C (7.0 ml) for a total of 35 ml. For the endpoint package, any participants who are concerned about the volume of blood should be reassured that the total amount of blood is 1/15th of the volume given in a typical Red Cross blood collection (450 ml). Each endpoint package should be collected after an 8-hour fast with sample collection occurring between 7-10 a.m.

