In accordance with OSHA regulations on blood borne pathogens (see appendix for the complete OSHA regulations), the following laboratory safety protocol for field-center laboratories is recommended: Use of non-permeable lab coats, Latex gloves, and face shields when handling any blood in any situation where splashes, spray, splatter, or droplets of blood may be generated and eye, nose, mouth contamination can be reasonably anticipated. Follow universal precautions when handling any blood products. Contaminated needles and sharps shall be immediately placed in a puncture-resistant, leak-proof container. Never re-cap or break needles. Hepatitis B vaccine should be offered to all technicians handling blood.

2. Phlebotomy area:

The blood drawing area should take place in an isolated room or participants should be separated by room dividers. The room should be equipped with all the necessary blood drawing supplies. A separate counter or work cart should be equipped with all the materials and vials that are used for blood handling and processing. The centrifuge, refrigerator, and freezer should be near by.

3. Participant preparation:

Informed consent must be obtained before drawing blood. This procedure is followed to ensure that the subjects understand the purpose of blood drawing and the possible complications of venipuncture. A standard informed consent has been prepared for

this study. With regard to laboratory procedures, the consent statement informs study subjects that there is a small risk of bruising at the spot on the arm where the blood is taken and that about 2 tablespoons of blood are drawn. The consent statement also informs study subjects that they will be contacted if clinically important test results are abnormal.

4. Participant phlebotomy question:

Minimal fasting time required for testing is 8 hours (optimum is 12 hours), and all samples for endpoint package should be collected between 6-10 a.m. Record the time of last food and the time of blood drawing. If the participant is not fasting, the blood sample will not be drawn and the subject should be rescheduled for phlebotomy within the next three days. Similarly, if the collection time is outside the 6-10 a.m. period, the subject should be rescheduled for phlebotomy.

5. General:

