Blood drawing is standardized for the sitting position. The venipuncture performed with the 21-gauge butterfly needle with 12 inches of plastic tubing between the venipuncture site and the blood collection tubes. The butterfly is a small, thin-walled needle which minimizes trauma to the skin and vein. The use of 12 inches of tube allows tubes to be changed without any movement of the needle in the vein. If the participant is concerned about the venipuncture, he/she may be reassured to know that such care is taken. The participant should be given enough time to feel comfortable both before and after the blood collection. In many cases, the most memorable part of the experience for the participant will be the contact with the person who draws the blood and their general attitude and competence. If the participant is nervous or excited, the technician briefly describes the procedure; e.g., "I am going to be drawing about 2 tablespoons of blood. This blood will be used for tests for lipids and cholesterol and blood clotting factors."

HANDLING PARTICIPANTS WHO ARE EXTREMELY APPREHENSIVE ABOUT HAVING BLOOD DRAWN.

Do not under any circumstances force a participant to have blood drawn. It may help to explain to the participant that the blood drawing is designed to be as nearly painless as possible. It is sometimes best to let the participant go on with another part of the examination. It may also be helpful to have the participant relax in the blood drawing chair just so the phlebotomist can check the veins in the participant's arms, without actually drawing blood.

6. Venipuncture procedure: Wear Latex gloves and lab coat

a) Arrange draw tubes in order of draw on the table top within easy reach. Assemble butterfly apparatus and vacutainer holders, gauze, and alcohol prep prior to tourniquet application.

b) Apply tourniquet to either arm.

- c) Examine participant's arms for the best site for venipuncture. Release tourniquet.
- d) Cleanse venipuncture site. Prepare area by wiping with alcohol swab in a circular motion from center to periphery. Allow area to dry.
- e) Reapply tourniquet and start timer.
- f) Grasp the participant's arms firmly using your thumb to draw the skin taut. This anchors the vein. The thumb should be one or two inches below the venipuncture site.
- g) With the needle bevel upward, enter the vein with a smooth continuous motion.

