(4) Paragraphs (d)(2) Engineering and Work Practice Controls, (d)(3) Personal Protective Equipment, (d)(4) Housekeeping, (e) HIV and HBV Research Laboratories and Production Facilities, (f) Hepatitis B Vaccination and Post-Exposure Evaluation and

Follow-up, and (g) (1) Labels and Signs, shall take effect July 8, 1992.

[FR Doc. 91-23866 Filed 12-2-91; 8:45 am]
BILLING CODE 4810-26-M

DELTA

Materials for center to have at time of training:

6/7/93

For safety

1. Institutional OSHA training policy, institutional procedures
2. Appropriate safety supplies for a phlebotomy station. OSHA acceptable personal protective equipment, appropriate disposal units for sharps and regulated medical waste, supplies for cleaning spills, etc.)

For Cholestech operation

1. Cholestech instrument, printer, paper, Optic check cassette, manual.
Materials for fingerstick blood draw (lancets, alcohol swabs, etc.)
Practice cassettes
2. Copy of procedure (supplied by [name])

For Baseline samples.

1. Phlebotomy supplies for drawing 4 Vacutainers - Vacutainer adapter and Vacutainers.
Vacutainers: 2 6-mL SST tubes (Becton Dickinson 367784)
1 3-ml lavender top (EDTA) (Becton-Dickinson 367661)
1 10 ml lavender top (EDTA) (Becton-Dickinson 6457)
2. Clinical centrifuge, transfer pipets, supplies. (Are also needed for endpoint samples. See attachments describing supplies for endpoint samples)
3. 2 Amber cryovials (0.5 ml) for buffy coats (e.g. Sarstedt 72.730.008)

DELTA

Materials for center to have at time of training (cont):
6/7/93

For endpoint samples

1. Blood collection tray - Supplies for drawing 5 Vacutainers. (See Chapter 10, p. 11, attached - Blood Collection Rack and Blood collection tray checklist)
Vacutainers: 2 9.5 mL SST (Becton-Dickinson 6510)
 2 4.5 ml blue top (citrate) (Becton-Dickinson 6418)
 1 10 ml lavender top (EDTA) (Becton-Dickinson 6457)
2. Equipment and supplies for sample processing and aliquoting including:
 - a. Two centrifuges (one refrigerated and one room temperature) with holders for Vacutainers and capable of at least 1500xg (preferably 3000xg).
 - b. 500 ul MLA pipet
 - c. Other supplies and equipment as listed from Chapter 10 (attached)
3. Supplies for archiving and shipping samples

For each subject endpoint sample

- 28 0.5 ml cryovials (Sarstedt #72.730.003) without caps
- 14 red caps - Sarstedt #65.716.003
- 4 green caps - Sarstedt #65.716.005
- 4 blue caps - Sarstedt #65.716.001
- 6 lavender caps - Sarstedt #65.716.008

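### Staff are told to describe an endpoint blood draw as 1/15th of a 450 ml donation (30 ml), but the protocol's own tubes total 35 to 36 ml, about 1/13th

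*Protocol*

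**What the plan says.** Chapter 8, II.A gives the endpoint draw three ways.

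- The opening sentence has "approximately 36 ml of blood four times at the end of each diet phase".
- The tube-by-tube description ends with "an EDTA-plasma tube at 4°C (7.0 ml) for a total of 35 ml".
- The next sentence begins "For the endpoint package, any participants who are concerned about the volume of blood" and continues that they "should be reassured that the total amount of blood is 1/15th of the volume given in a typical Red Cross blood collection (450 ml").

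The venipuncture section repeats a low figure in two places. Under participant preparation (II.B.7.d.3), the consent statement is described as telling subjects that "about 2 tablespoons of blood are drawn". Under the general instructions (II.B.7.d.5), the technician's suggested words to a nervous participant are "I am going to be drawing about 2 tablespoons of blood", for lipid, cholesterol and clotting tests.

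The tube volumes are not uniform either. The endpoint EDTA tube is 7 ml throughout the text of Chapter 8, but the supply list for endpoint samples in the training materials (dated 6/7/93) asks for "1 10 ml lavender top (EDTA) (Becton-Dickinson 6457").

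**The concern.** Two adjacent sentences in II.A cannot both be right. If the package is 35 ml it is not 1/15th of 450 ml, and if it is 1/15th it is not 35 ml. The fraction is an instruction on what to tell a participant who has asked about volume, so it is not background text. Anyone who relies on it is given a smaller number than the protocol plans to draw, at each of twelve draws.

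What is at stake is the accuracy of a statement made to participants, together with consistency in what the centers stock. No study result is at stake.

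**Working it through.** **Inputs from the protocol**

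- Reference donation 450 ml and stated fraction 1/15 (II.A).
- Endpoint tubes in II.A and in the processing limits (III.I): 9.5, 9.5, 4.5, 4.5 and 7.0 ml.
- Endpoint tubes in Figures 1 and 2 and in the draw order (II.B.5): 10, 10, 4.5, 4.5 and 7.0 ml.
- Endpoint tubes in the training supply list: 9.5, 9.5, 4.5, 4.5 and 10 ml.
- Each 4.5 ml blue-stopper tube contains 0.5 ml of citrate (II.B.4).
- Four endpoint packages on each of three diets, and 25.5 ml at baseline (II.A).

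Assumption: one tablespoon is 14.8 ml. Using 15 ml leads to the same conclusion.

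**The protocol's figure**

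450 / 15 = 30 ml. Two tablespoons is 2 × 14.8 = 29.6 ml, so the fraction and the tablespoon wording agree with each other.

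**The same quantity from the tube volumes**

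| Source | Sum (ml) | Fraction of 450 ml | Shortfall of 30 ml |
|---|---|---|---|
| II.A tube list, III.I | 9.5+9.5+4.5+4.5+7 = 35 | 450/35 = 12.9, so 1/12.9 | 5 ml; 5/35 = 14.3% |
| Figures 1 and 2, II.B.5 | 10+10+4.5+4.5+7 = 36 | 450/36 = 12.5, so 1/12.5 | 6 ml; 6/36 = 16.7% |
| II.A list, counting 4.0 ml of blood per citrate tube | 9.5+9.5+4+4+7 = 34 | 450/34 = 13.2, so 1/13.2 | 4 ml; 4/34 = 11.8% |
| Training supply list | 9.5+9.5+4.5+4.5+10 = 38 | 450/38 = 11.8, so 1/11.8 | 8 ml; 8/38 = 21.1% |

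No five-tube reading reproduces 30 ml; the lowest is 34 ml. Taking only the three tubes that II.B.5 calls absolute priority gives 9.5 + 4.5 + 4.5 = 18.5 ml, which does not give 30 ml either.

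Section II.B.5 also disagrees with itself slightly. It states about 35 ml, but the tubes it lists sum to 36 ml. The 1 ml difference comes from calling the two serum tubes 9.5 ml in some places and 10 ml in others.

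**In tablespoons**

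35 / 14.8 = 2.4 and 36 / 14.8 = 2.4.

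**Cumulative volume, for information**

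12 × 35 + 25.5 = 445.5 ml and 12 × 36 + 25.5 = 457.5 ml. These are 445.5 / 450 = 0.99 and 457.5 / 450 = 1.02 of a donation. The protocol states no cumulative figure in the text available, so there is nothing to reproduce or contradict.

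**The case against.** The strongest reply is that this is one wrong fraction worth 5 to 6 ml, in a trial that lays out its tubes and draw schedule openly. That is correct, and it sets the size of the point. Several larger readings that a reader might infer do not hold.

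- **That one draw is presented as the study total.** The sentence is expressly limited to the endpoint package, and its total is the sum of the five tubes. The cumulative 446 to 458 ml therefore contradicts no stated figure.
- **That repeated sampling is concealed.** Section II.A and Figure 1 list four packages on each of three diets, and the telephone script tells applicants that blood is taken in weeks 5, 6, 7 and 8 of each diet period. The consent pages are not in the available text, so nothing can be said about whether they give a total.
- **That 2 tablespoons is an arithmetic error.** The wording is approximate, and 2.4 rounds to 2. The venipuncture section also serves the baseline draw, and 25.5 / 14.8 = 1.7 tablespoons rounds to 2 as well. The technician's words mention clotting factors, so they do fit the endpoint draw, where the figure is low, but still as loose rounding.
- **That the draw is really 38 ml.** This rests on one line of a training supply list. The overview, both figures, the tube descriptions, the draw order, the centrifugation balance tubes and the processing limits all give 7 ml for the endpoint EDTA tube.
- **That the hematology rationale is wrong.** Section I.C.10 says these measures "should be monitored at baseline to assure that the subject will not suffer untoward effects from serial phlebotomy". It gives no volume and makes no statement that the arithmetic above contradicts.

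What remains is that the fraction is wrong, it is given to participants, and it errs low on every full-package reading.

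**Conclusion.** The statement that an endpoint package is 1/15th of a 450 ml donation is wrong. On the protocol's own volumes it is about 1/12.9 (35 ml) to 1/12.5 (36 ml), so each draw is understated by 5 to 6 ml, or 14 to 17%. Counting the citrate separately narrows the gap to 4 ml (12%) without closing it. The conclusion rests only on nominal tube volumes and the 450 ml reference in the same section; the tablespoon size matters only for the rounding remark.

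Two smaller inconsistencies go with it: 35 against 36 ml for the same package, and a 7 ml against a 10 ml endpoint EDTA tube. Severity is minor. No endpoint, power calculation or analysis is affected. A reader might infer from the cumulative sum that the stated burden of the whole study is misreported. The documents do not support that, because no study total is stated.

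**What to change.** 1. Use one endpoint volume throughout Chapter 8 (II.A opening sentence, II.A tube list, Figures 1 and 2, II.B.4, II.B.5, III.I), including one nominal size for the serum tubes.
2. Reconcile the 10 ml endpoint EDTA tube in the training supply list with the 7 ml tube in the text, so that centers stock what the protocol describes.
3. Restate the reassurance in II.A from the reconciled volume. At 35 to 36 ml that is about 1/13th of a 450 ml donation (1/12.9 to 1/12.5).
4. Change about 2 tablespoons to about 2½ in II.B.7.d.3 and II.B.7.d.5, and check the consent form for the same wording.
5. Optionally, add that 12 endpoint draws plus the 25.5 ml baseline come to about 446 to 458 ml, roughly one donation. This adds disclosure; it corrects no existing statement.

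The cost is a few words in the manual, the technician's script and possibly the consent form, plus one line of the supply list. The per-draw figure told to participants becomes slightly larger.
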